15.6 Interim Analysis

Original Study Design: An interim efficacy analysis will be conducted after 40 patients are randomized to each sequence (a total of 80 patients). Given that the interim analysis will primarily focus on the complete response endpoint, study accrual will be suspended for approximately 2 weeks while the initial outcome data from all patients is collected. This interim analysis will allow early accrual termination for efficacy or for futility.

The O'Brien-Fleming analogue will define the alpha and beta spending function. The group sequential procedure for proportions within PASS has been used to simulate the following boundaries for comparing the CR rate in the two groups using a large-sample Z-test. 19,20

| | Significance Boundary | | Futility Boundary | | |
|------------------------|-----------------------|---------------|-------------------|---------------|--|
| Look | Z-Value Scale | P-value Scale | Z-Value Scale | P-Value Scale | |
| 1 (after 80 patients) | 2.505 | 0.006 | 0.325 | 0.373 | |
| 2 (after 160 patients) | 1.657 | 0.049 | 1.657 | 0.049 | |

At the time of the interim analysis, the combination would be considered superior to ondansetron monotherapy if the p-value was less than 0.006 and accrual terminated. If, on the other hand, the p-value associated with this comparison was 0.373 or larger, there would be a recommendation that accrual be terminated early due to futility.

These boundaries will be used as guidance in determining whether patient accrual should be terminated early. Other issues may also factor into that decision-making.

Modified Study Design: With the reduction in the study's accrual target as described in Section 15.4, no interim analyses are planned.

15.7 Sample Size Calculation

15.7.1 Original Study Design

One hundred seventy (170) glioma patients will be enrolled with the expectation that 160 patients will be randomized to receive one of two treatment sequences of anti-emetic therapy for the prevention of nausea and vomiting associated with RT and concomitant TMZ. A permutated block randomization with an allocation ratio of 1:1 will be used to assign patients to sequence A or B. Sequence A involves a 3-week regimen of daily ondansetron followed by a 3-week regimen consisting of rolapitant (day 22 only) and daily ondansetron; whereas Sequence B involves a 3-week regimen of rolapitant (day 1 only) and daily ondansetron followed by a 3-week regimen of daily ondansetron. The study has one primary and one KEY secondary endpoint: CR rate and patient overall preference for ondansetron treatment with or without rolapitant. Though the primary CR rate endpoint will focus on treatment during the first 2 weeks of RT and TMZ, a crossover design is proposed so that a patient will experience both modes of treatment, and be equipped to make a comparative assessment of preference.

Power Calculations for Complete Response, Primary Endpoint: The power of the comparison of ondansetron and the combination of ondansetron and rolapitant relative to the CR rate during the initial 2 weeks of treatment with RT and TMZ will be considered here. This comparison will focus on the anti-emetic experience during the first regimen of the two treatment regimens that the patient will receive. Let

p₁ = overall complete response rate for the first 2 weeks of treatment with the combination antiemetic regimen, and

 p_0 = overall complete response rate during the first 2 weeks of treatment with ondansetron alone.

The hypothesis that will be assessed is whether the CR rate with combination treatment is greater than that with ondansetron alone. Specifically, the hypothesis that will be tested is as follows:

 H_0 : $p_1 \le p_0$ versus H1: $p_1 > p_0$

Temozolomide prescribing information reports a vomiting rate of 20% with concomitant RT + TMZ. Anti-emetic treatment failure includes the occurrence of vomiting or the use of an anti-emetic for nausea and/or vomiting. Therefore, we anticipate that approximately 25% of patients receiving ondansetron alone to either vomit or receive an anti-emetic. Equivalently, a CR rate of 75% is anticipated with ondansetron alone.

One hundred sixty (160) patients will be randomized to either sequence A or B with the expectation that 152 patients will provide an assessment of their experience during the first 2 weeks of treatment with the first regimen. With 152 patients, there is 80% power to detect an increase in the CR rate from 75% with ondansetron to 90% with the combination of ondansetron and rolapitant (α =0.05; one-tailed).

Power Calculations for Patient Preference, KEY Secondary Endpoint: The hypothesis of this study is that patients will prefer the combination of ondansetron and rolapitant over ondansetron alone for the prevention of nausea and vomiting. If no overall preference exists, then the percentage of patients who choose combination treatment is expected to be approximately 50%. The hypothesis that will be tested is whether the proportion of patients who prefer combination treatment is greater than 50%. Statistically, the hypothesis that will be tested is:

H0: $p \le 0.5$ vs H1: p > 0.5

where p is the proportion of patients who prefer combination treatment over ondansetron alone. Under the assumption that approximately 140 patients will have experienced both regimens and provided a preference assessment, the study has 93% power to detect a preference rate of 65% or greater with a two-tailed test conducted at the 0.05 level of significance.

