15.5.1 Key Secondary Objective

The percentage of patients who prefer rolapitant plus ondansetron over ondansetron, as determined by response to the question with "Which nausea medication regimen was I most satisfied with?" will be calculated, with a 95% confidence interval. An exact binomial test assessing whether the proportion preferring the treatment regimen that includes rolapitant is 0.5 will be conducted. Logistic regression will explore the potential that sequence influences patient preference.

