15.7.2 Modified Study Design

As described in Section 15.4, the sample size goal for this study is reduced to 57 patients. With 57 patients, there is 80% power to detect an increase in the CR rate from 75% with ondansetron to 97% with the combination of ondansetron and rolapitant (α =0.05; one-tailed). Alternatively, there is 80% power to detect an increase in CR rate from 63% to 90%.

Relative to patient preference, with 57 patients, the study has 83% power to detect a preference rate of 69% or greater with a two-tailed test conducted at the 0.05 level of significance.

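### The key secondary preference hypothesis is written one-sided but powered two-tailed at 0.05, and the analysis section states neither direction nor alpha

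*Combined protocol and SAP*

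**What the plan says.** Three places in the combined protocol and SAP bear on the test of preference.

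- **Section 15.7.1** gives the hypothesis in words, "The hypothesis that will be tested is whether the proportion of patients who prefer combination treatment is greater than 50" percent, and in symbols, H0: p ≤ 0.5 versus H1: p > 0.5. It then assumes that "approximately 140 patients will have experienced both regimens and provided a preference assessment" and claims "93% power to detect a preference rate of 65% or greater with a two-tailed test conducted at the 0.05 level of significance".
- **Section 15.7.2**, the current design, says that "with 57 patients, the study has 83% power to detect a preference rate of 69% or greater with a two-tailed test", again at the 0.05 level.
- **Section 15.5.1**, the analysis section, says "An exact binomial test assessing whether the proportion preferring the treatment regimen that includes rolapitant is 0.5 will be conducted". It also calls for a 95% confidence interval. It states no direction, no alpha and no interval method.

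The primary endpoint has a hypothesis of the same form in 15.7.1 (H0: p1 ≤ p0 versus H1: p1 > p0), and its power is explicitly one-tailed at 0.05 in both 15.7.1 and 15.7.2.

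**The concern.** A directional alternative and a two-tailed test have different rejection regions unless the alpha for the directional test is halved, and the plan does not say that it is. The section an analyst would follow, 15.5.1, does not settle the matter. The primary endpoint gives a ready precedent in the same document: a hypothesis of the same shape, tested one-tailed at 0.05. An analyst could carry that over to preference in good faith.

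At stake is the threshold at which the only key secondary endpoint is called positive. The two forms also differ in what they allow to be concluded. A two-tailed test can support a finding that patients prefer ondansetron alone; a test of H0: p ≤ 0.5 cannot. The trial is unblinded (section 9.6) and now small, so it is better to have the rule in one place before the preference data are analysed.

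**Working it through.** **Inputs.** Null value 0.5 (15.5.1, 15.7.1). Original design: n = 140, alternative 0.65, stated power 93%, two-tailed 0.05 (15.7.1). Modified design: n = 57, alternative 0.69, stated power 83%, two-tailed 0.05 (15.7.2). Test: exact binomial (15.5.1). One-sided 0.05 for preference is my assumption, borrowed from the primary endpoint.

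**Method.** With X ~ Binomial(n, p), the upper cut-off r is the smallest count with P(X ≥ r | n, 0.5) ≤ a, where a = 0.05 for one-sided 0.05 and a = 0.025 for two-sided 0.05. Power is P(X ≥ r) at the alternative, plus the lower tail P(X ≤ n − r) for the two-sided test.

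**Step 1: the plan's 93% at n = 140 and 65%.**

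| Test | Cut-off | Upper tail at 0.5 | Power at 65% |
|---|---|---|---|
| Exact two-sided 0.05 | 83 | 0.0171 | 93.3% |
| Exact one-sided 0.05 | 81 | 0.0378 | 96.7% |

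The two-sided exact test reproduces the stated 93%; one-sided 0.05 does not. A one-sided test at 0.025 has the same cut-off of 83 and the same 93.3%, so this match rules out one-sided 0.05 but does not by itself separate two-sided 0.05 from one-sided 0.025.

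**Step 2: the plan's 83% at n = 57 and 69%.**

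| Test | Cut-off | Upper tail at 0.5 | Power at 69% |
|---|---|---|---|
| Exact two-sided 0.05 | 37 or more (or 20 or fewer) | 0.0166 | 79.3% |
| Exact one-sided 0.05 | 36 or more | 0.0314 | 86.3% |

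Neither exact test gives 83%. A two-sided normal approximation comes close:

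Φ{[(0.69 − 0.5)·√57 − 1.96·0.5] / √(0.69·0.31)} = Φ{(1.434 − 0.980) / 0.4625} = Φ(0.983) = 83.7%.

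The same approximation at n = 140 gives 95.2%, not 93%. The figure in 15.7.1 therefore agrees with the exact test, and the one in 15.7.2 only with an approximation.

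**Step 3: where the readings part at n = 57.**

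| Count | One-sided p | Two-sided p | One-sided 0.05 | Two-sided 0.05 |
|---|---|---|---|---|
| 35 | 0.0556 | 0.1112 | negative | negative |
| 36 | 0.0314 | 0.0627 | positive | negative |
| 37 | 0.0166 | 0.0331 | positive | positive |

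They differ at 36 only. The chance of exactly 36 is 86.3% − 79.3% = 7.0% at the 69% alternative, and 0.0314 − 0.0166 = 0.0148, about 1.5%, at p = 0.5.

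**Step 4: fewer answers.** Section 15.1 restricts this analysis to patients who experienced both regimens and gave a preference, so n may fall below 57. From n = 40 to 56 the readings differ at one count, except at n = 53, where the cut-offs are 33 and 35 and they differ at 33 and 34. At n = 53 the chance of landing on either is 88.5% − 73.4% = 15.1% at 69%.

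**The case against.** The strongest reply is that the plan never states a one-sided 0.05 test of preference. The only alpha attached to this endpoint is two-tailed 0.05, given in both 15.7.1 and 15.7.2. The authors label the primary endpoint one-tailed, so they plainly distinguished the two. Section 15.5.1 tests a point null, which reads most naturally as two-sided. A directional hypothesis can also be reconciled with a two-tailed 0.05 test by reading it as one-sided at 0.025: the upper cut-offs are then identical (37 of 57, 83 of 140) and 36 of 57 is negative either way.

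All of this stands, and it limits the point. It shows that two-sided 0.05 is the likelier intent. It does not remove the written alternative p > 0.5, described as the hypothesis to be tested, or supply the direction and alpha missing from 15.5.1. The 0.025 reading reconciles the text, but 0.025 appears nowhere for this endpoint.

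The narrowness also stands: one count at n = 57, on a secondary endpoint, in a trial whose text already warns of lost power (15.4), with an estimate and interval to be reported regardless.

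**Conclusion.** The inconsistency is real and should be corrected, but its reach is small. The written hypothesis is one-sided, the stated power is two-tailed at 0.05, and the analysis section is silent on both direction and alpha. The verdict changes only if the one-sided hypothesis is tested at 0.05, and then at 36 of 57, or at 33 and 34 of 53.

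Three stronger readings are not supported:

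- A reader might infer that the result can be freely chosen once the data are seen. Two-tailed 0.05 is written down in advance in two places, and a one-tailed 0.05 analysis would contradict both.
- A reader might infer that the 93% proves two-sided 0.05 was meant. One-sided 0.025 gives the same cut-off and power.
- A reader might add the choice of confidence interval to the size of this problem. At 36 of 57 a Wald interval (50.6% to 75.7%) excludes 50% and the Clopper-Pearson interval (49.3% to 75.6%) includes it, but both are two-sided. That gap comes from the unnamed interval method, not from the direction of the test.

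A related error is firmer: the 83% in 15.7.2 is not the power of the exact test named in 15.5.1, which is 79.3% at two-sided 0.05. Even that assumes all 57 patients give a preference.

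**What to change.** Change three places, before the preference data are analysed:

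- **15.5.1:** state a two-sided exact binomial test of p = 0.5 at the 0.05 level, with an exact (Clopper-Pearson) 95% confidence interval. Naming the interval makes it agree with the test.
- **15.7.1:** restate the hypotheses as H0: p = 0.5 versus H1: p ≠ 0.5. This fits the two-tailed test and the 93% already stated there.
- **15.7.2:** restate the power at 57 patients and a 69% preference rate as about 79% for that exact test, in place of 83%.

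The cost is wording only, with no new data or procedures. The sponsor gives up the easier one-sided 0.05 threshold (36 instead of 37 of 57) and reports a power about four points lower (83% − 79%).

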15.7.2 Modified Study Design

As described in Section 15.4, the sample size goal for this study is reduced to 57 patients. With 57 patients, there is 80% power to detect an increase in the CR rate from 75% with ondansetron to 97% with the combination of ondansetron and rolapitant (α =0.05; one-tailed). Alternatively, there is 80% power to detect an increase in CR rate from 63% to 90%.

Relative to patient preference, with 57 patients, the study has 83% power to detect a preference rate of 69% or greater with a two-tailed test conducted at the 0.05 level of significance.

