9.8 Definition of Evaluable Subjects, On Study, and End of Study

An evaluable subject is defined as a patient who meets eligibility criteria and completes at least two weeks of radiation for first CR and ~ 6 weeks of radiation for additional secondary outcomes.

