12.6.3 Replacement of Early Withdrawal(s)

Not applicable

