15.1 Analysis Sets

The analysis of the complete response endpoint will focus on all patients randomized to sequence A or B. However, the analysis of the patient preference endpoint will focus on those patients who have experienced both regimens and provided a preference assessment. Safety analyses will include all patients who receive protocol treatment.

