15.4 Primary Objective

The primary objective of this study is to compare the efficacy of rolapitant plus ondansetron vs. ondansetron alone in the prevention of nausea and vomiting, as measured by the overall complete response rate, among malignant glioma patients during RT and concomitant TMZ (see Section 8).

As described in Sections 15.6 and 15.7, the study was originally designed to enroll 170 glioma patients with the expectation that 160 patients would be randomized to receive one of two treatment sequences of anti-emetic therapy for the prevention of nausea and vomiting associated with RT and concomitant TMZ. A formal interim analysis was planned after 80 patients had been randomized (i.e. 40 patients to each treatment sequence). As of mid-January 2022, 53 patients had been randomized. On January 18, 2022, TerSera, the study's funding source, requested that accrual to the study be terminated in the next few months.

Given this request from TerSera, the accrual target for this study is reduced to 57 patients. The decision to terminate early has not been influenced by the data collected to date, as no interim analyses have been conducted. The analyses as described below will be conducted; however, they may no longer have the power to detect the hypothesized effect size.

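### The 83% power stated for the preference endpoint is not the power of the planned exact test (79% with 57 assessments), and it allows for no missing preference assessments

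*Combined protocol and SAP*

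**What the plan says.** The power statement for the modified design, in section 15.7.2, reads "with 57 patients, the study has 83% power to detect a preference rate of 69% or greater with a two-tailed test" at the 0.05 level. It names no method and no expected number of assessments.

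Four other places bear on it:

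- **Test.** Section 15.5.1: "An exact binomial test assessing whether the proportion preferring the treatment regimen that includes rolapitant is 0.5 will be conducted".
- **Analysis set.** Section 15.1: "the analysis of the patient preference endpoint will focus on those patients who have experienced both regimens and provided a preference assessment". Section 9.8 likewise defines an evaluable subject as one who "completes at least two weeks of radiation for first CR and ~ 6 weeks of radiation for additional secondary outcomes". Section 12.6.3 marks replacement of early withdrawals as not applicable.
- **Meaning of 57.** Section 15.4: "the accrual target for this study is reduced to 57 patients".
- **Original design.** Section 15.7.1 randomized 160 patients but based its preference power on the assumption that "approximately 140 patients will have experienced both regimens and provided a preference assessment". It stated 93% power at a 65% preference rate, two-tailed at 0.05.

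**The concern.** There are two separate problems.

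First, an exact binomial test on 57 observations is conservative because the count is discrete, so its power can fall clearly below a large-sample figure. The stated 83% looked like a large-sample figure attached to an exact test.

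Second, the statement uses every accrued patient, although the endpoint exists only for patients who go through both treatment periods and answer the preference question at the end of week 6.

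Preference is the one key secondary endpoint, and section 15.7.1 gives the comparison of both regimens by the same patient as the reason for the crossover. After the cut in accrual, 15.7.2 is the only quantitative guide to reading a non-significant preference result. A power of 83% implies a 17% chance of missing a true 69% preference. The planned test has a larger chance of missing it.

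**Working it through.** **Inputs.** Null proportion 0.5 (15.5.1, 15.7.1); alternative 0.69 and n = 57 (15.7.2); two-sided alpha 0.05 (15.7.2); original design n = 140, alternative 0.65, stated power 93% (15.7.1); 160 randomized in the original design (15.7.1).

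**Step 1: where 83% may come from.** The large-sample formula, with the null variance in the critical value and the alternative variance in the power, is

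power = Φ{ [ (p − 0.5) − 1.96·√(0.25/n) ] / √( p(1 − p)/n ) }.

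At n = 57 and p = 0.69: √(0.25/57) × 1.96 = 0.1298 and √(0.69 × 0.31/57) = 0.0613, so power = Φ[(0.19 − 0.1298)/0.0613] = Φ(0.983) = 83.7%. With a continuity correction of 0.5/57 it is 79.9%. The uncorrected version is the closest match found to 83%, but the plan does not confirm it.

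**Step 2: the planned exact test.** Reject when 2·P(X ≥ c | n, 0.5) ≤ 0.05, and symmetrically in the lower tail. At n = 57:

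- 2·P(X ≥ 36) = 0.063, not rejected
- 2·P(X ≥ 37) = 0.033, rejected

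The test therefore rejects at 37 or more, or 20 or fewer, with actual size 0.033. Power = P(X ≥ 37 | 57, 0.69), plus a negligible lower tail, = **79.3%**.

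**Step 3: benchmark on the original figure.** At n = 140 and p = 0.65 the exact test rejects at 83 or more and has power 93.3%, which agrees with the stated 93%. The formula of step 1 gives 95.2% there. The original figure thus matches the planned test and the modified figure does not.

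**Step 4: size of the gap with all 57 assessments.** 83.0 − 79.3 = 3.7 percentage points. The exact test at n = 57 reaches 80% power at a true rate of about 69.2% and 83% at 69.8%.

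**Step 5: fewer than 57 assessments.** Exact power at a true 69%:

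| Assessments | Reject at or above | Power |
|---|---|---|
| 48 | 32 | 69.8% |
| 49 | 32 | 76.5% |
| 50 | 33 | 73.3% |
| 51 | 33 | 79.4% |
| 52 | 34 | 76.5% |
| 53 | 35 | 73.4% |
| 54 | 35 | 79.3% |
| 55 | 36 | 76.5% |
| 56 | 36 | 81.9% |
| 57 | 37 | 79.3% |

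The saw-tooth comes from the discreteness of the test. Over 44 to 57 assessments the maximum is 81.9% (at 56) and the minimum 66.0% (at 46).

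The modified design gives no retention rate. *Assumption:* the original share carries over, 140/160 = 87.5%. Then 57 × 0.875 = 49.9, about 50 assessments, with power **73.3%**. Averaged over a Binomial(57, 0.875) number of assessments, power is 74.6%. At n = 50, 80% power needs a true rate of about 70.4%.

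**The case against.** - **The gap is small and partly an effect of discreteness.** This is true with all 57 assessments. At 56 the exact power is 81.9% and at 58 it is 84.1%, and 83% is a usable large-sample approximation. Even so, the plan names the exact test, and no attainable count from 44 to 57 gives 83%. Rounding of the 69% does not help: a true 69.4% gives 81.1%.
- **The plan already warns of lost power.** Section 15.4 says that the analyses may lack power for the hypothesized effect. That general caution does not qualify the specific replacement figure in 15.7.2.
- **Sidedness is not stated in 15.5.1, and 15.7.1 writes a one-sided alternative.** Both power statements nevertheless specify a two-tailed test, and 15.7.2 does so in the words "with a two-tailed test conducted at the 0.05 level of significance". A one-sided exact test at 0.05 would have 86.3% power, so that reading does not give 83% either.
- **The second part is a missing assumption rather than an arithmetic slip, and 87.5% comes from a superseded design.** This stands. Every figure given here for about 50 assessments depends on that share. A Binomial(57, 0.875) count has a standard deviation of √(57 × 0.875 × 0.125) = 2.5, so 48 to 52 is less than one standard deviation either side of the mean and must not be read as the full plausible range.
- **The primary endpoint has the same omission.** Section 15.7.1 used 152 of 160 patients for complete response, and 15.7.2 uses all 57. This is a fair observation, but it does not weaken the point on preference.

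**Conclusion.** The concern holds in both parts. The planned exact test, two-sided at 0.05, has 79.3% power at a true 69% with 57 assessments, against the stated 83%. That result rests only on the plan's own inputs.

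The figure of 57 also treats every accrued patient as contributing a preference, which the analysis set does not guarantee and the original design did not assume. If the original 87.5% share applies, power is about 73%, roughly 10 points below the stated value, and the chance of missing a true 69% preference is about 27% instead of 17%.

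The first part alone would be a minor correction. The second can matter more, but its size depends on a retention rate that the modified design does not give. Neither part affects the validity of the test itself.

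**What to change.** Restate the preference paragraph of section 15.7.2 along these lines:

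> With 57 preference assessments, the exact two-sided binomial test at the 0.05 level has 79% power at a preference rate of 69%. If about 87.5% of patients provide an assessment, as assumed in the original design (about 50 patients), power is about 73% (70% to 79% for 48 to 52 assessments), and 80% power with 50 assessments requires a preference rate of about 70.4%.

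Keep the range tied explicitly to 48 to 52 assessments, or quote 66% to 82% for 44 to 57. If the number of patients who gave a preference is already known, use that count in place of the 87.5% assumption. State in 15.5.1 that the exact test is two-sided, to agree with 15.7.

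The cost is text only. The test, the analysis set and the sample size are unchanged; the stated power becomes less favourable.
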